#### **8.1.6.5 Frequentist analysis – Mixed Model Repeated Measures with Baseline by treatment group interaction**

A frequentist analysis of the change from Baseline in ASDAS will be performed using a MMRM as specified in [Section 8.1.6.4](#). In addition, the model will include the Baseline ASDAS by treatment group interaction.

The results presentation, and the covariance matrix structures, as specified in [Section 8.1.6.4](#), will be applied.

### **8.2 Secondary efficacy variables**

Secondary efficacy variables will be listed and summarized by treatment group and visit for the PPS and repeated for the FAS.

#### **8.2.1 ASDAS Disease Activity States and Improvement**

##### **8.2.1.1 Derivation of ASDAS Disease Activity States and Improvement**

Cut-offs for 4 disease activity states based on ASDAS will be defined for each subject at Baseline and at each post-Baseline visit as follows:

- ASDAS-Inactive Disease (ASDAS-ID): ASDAS < 1.3
- ASDAS-Moderate Disease activity (ASDAS-MD): ASDAS  $\geq$  1.3 to < 2.1
- ASDAS-High Disease activity (ASDAS-HD): ASDAS  $\geq$  2.1 to  $\leq$  3.5
- ASDAS-Very High Disease activity (ASDAS-vHD): ASDAS > 3.5

In addition, the following cut-offs for 2 levels of improvement in ASDAS will be defined for each subject at each post-Baseline visit based on the change from Baseline in ASDAS:

- ASDAS Clinically Important Improvement (ASDAS-CII): a reduction (improvement) from Baseline in ASDAS  $\geq$  1.1 units
- ASDAS Major Improvement (ASDAS-MI): a reduction (improvement) from Baseline in ASDAS  $\geq$  2.0 units

ASDAS-Inactive Disease (ASDAS-ID) and ASDAS-Major Improvement (ASDAS-MI) at Week 12 are the secondary efficacy variables defined for this study. Subjects with missing ASDAS at Week 12 will not be classified in terms of their ASDAS disease activity state or improvement according to the above definitions.

##### **8.2.1.2 Analysis of ASDAS Disease Activity States and Improvement**

The number and percentage of subjects classified in each of the disease activity state categories (ASDAS-ID, ASDAS-MD, ASDAS-HD and ASDAS-vHD) and each disease improvement category (ASDAS-CII [yes/no] and ASDAS-MI [yes/no]) and will be tabulated by treatment group and visit including the 95% CIs calculated using a Wilson approximation.

Additionally, inferential treatment effects for ASDAS-ID and ASDAS-MI at Week 12 will be derived from the Bayesian analysis as described in [Section 8.1.2.1](#). ASDAS-ID and ASDAS-MI rates at Week 12 will be presented.

## 8.3 Other efficacy variables

### 8.3.1 Derivation of Assessment in SpondyloArthritis International Society Response

The following ASAS-based variables will be derived:

- ASAS20 response is defined as an improvement of at least 20% (percentage change from Baseline of -20% or more negative), and an absolute improvement of at least 1 unit (change from Baseline of -1 or more negative) in at least 3 of the 4 following domains:
  - PGADA ([Section 8.1.5.2](#))
  - Function (represented by BASFI, [Section 8.3.3.1](#))
  - Pain assessment (the total spinal pain NRS score, [Section 8.3.3.2](#))
  - Inflammation (the mean of the BASDAI Questions 5 and 6 results, [Section 8.1.5.1](#), concerning morning stiffness intensity and duration)

In addition, *absence* of deterioration in the potential remaining domain is required. Deterioration is defined as the presence of both of the following:

- percentage change from Baseline of 20% or more;
- change from Baseline of 1 unit or more.
- The ASAS40 response is defined as an improvement of at least 40% (percentage change from Baseline of -40% or more negative), and an absolute improvement of at least 2 units (change from Baseline of -2 or more negative) in at least 3 of the 4 domains above. In addition, no worsening (a change from Baseline that is non-positive [ie, negative or zero]) in the remaining domain is required.
- Time to ASAS20 response: defined as the time (in days) from the first dose of IMP to the first instance (if more than one instance) of an ASAS20 response.
  - This will be calculated for the Treatment Period and across the entire study period (Treatment Period + Treatment Extension Period) separately.
  - For time to ASAS20 response during the Treatment Period:
    - Subjects who discontinue early prior to an ASAS20 response will be censored on the date of their last efficacy assessment during the Treatment Period.
    - Subjects who do not have an ASAS20 response during the Treatment Period will be censored on the date of their Week 12 efficacy assessment (ie, end of the Treatment Period).
  - For time to ASAS20 response during the study (Treatment Period + Treatment Extension Period):

- Subjects who discontinue early prior to an ASAS20 response will be censored on the date of their last efficacy assessment during the study (Treatment Period + Treatment Extension Period).
- Subjects who do not have an ASAS20 response during the study will be censored on the date of their Week 48 efficacy assessment (ie, end of the Treatment Extension Period).
- Time to ASAS40 response: defined as the time (in days) from the first dose of IMP to the first instance (if more than one instance) of an ASAS40 response. As described above for time to ASAS20 response, time to ASAS40 response will be calculated based on the Treatment Period and also across the study period (Treatment Period + Treatment Extension Period) separately and the same censoring rules will be applied.
- The ASAS partial remission (ASAS-PR) response is defined as a score of  $\leq 2$  units in all 4 domains listed above.

In order for a subject to be defined as a responder (ASAS20, ASAS40 or ASAS-PR, respectively) at a given visit, the criteria stated must be met all together that visit.

Missing component data for the derivation of the ASAS20, ASAS40 and ASAS-PR will be handled as described in [Section 4.2.1.4](#).

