5.1.3 Treatment Extension Period (Week 12 to Week 48)

After completing the 12-week Treatment Period, subjects will enter a 36-week Treatment Extension Period and will receive the following treatments:

- Subjects randomized to bimekizumab during the Treatment Period will receive bimekizumab 320mg sc Q4W from Week 12 to Week 44.
- Subjects randomized to CZP during the Treatment Period will receive CZP 400mg Q4W from Week 12 to Week 44.

Subjects not responding to treatment during the Treatment Period will be withdrawn from the study as per Investigator's discretion and will not enter the Treatment Extension Period.

The assessments during the Treatment Extension Period are presented in [Table 5–1](#).

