5.9 Rationale for study design and selection of dose

AS0013 is a Phase 2a, multicenter, randomized, subject-blind and investigator-blind study to evaluate the efficacy and safety of bimekizumab and CZP in adult subjects with active AS. AS0013 includes a 12-week Treatment Period, a 36-week Treatment Extension Period, and a 20-week SFU Period. Rationales for the study design, selected population, and bimekizumab doses are provided below.

Study design

AS0013 was designed to evaluate the efficacy, safety and the process of osteoproliferation using PET imaging techniques at Screening and after 12 and 48 weeks of treatment. The scientific rationale suggesting a role for IL-17A treatment in bone formation as compared to TNF α treatment is provided in detail in [Section 2.4](#).

While the primary evaluation will be conducted after 12 weeks, a 36-week Treatment Extension Period has been added in order to maintain the treatment blind after subjects have reached Week 12 (ie, the evaluation of the primary efficacy variable) and to allow continued access to IMP for subjects responding to treatment. This extension also allows further evaluation of the inhibition of the osteoproliferative effect of bimekizumab and CZP at Week 48 and to compare this to Baseline and Week 12.

Population

AS0013 was designed to evaluate the potential benefit of bimekizumab to prevent bone formation in subjects at risk of new bone formation (disease progression) and comparing the outcome to treatment with CZP. Inclusion criteria will ensure that all subjects have active AS. Some exclusion criteria are intended to eliminate subjects who may present an unacceptable safety risk were they to participate in this investigational study program. Active AS is defined by a BASDAI score ≥ 4 and a spinal pain score ≥ 4 (from BASDAI Question 2). The full list of inclusion and exclusion criteria is provided in [Section 6](#).

Dose selection

The following dose regimens of bimekizumab and CZP will be evaluated during the Treatment Period:

- Bimekizumab 160mg sc Q2W from Week 0 through Week 10
- CZP 400mg sc Q2W at Weeks 0, 2, and 4 (loading dose) followed by CZP 200mg sc Q2W in Weeks 6 to 10.

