#### **8.3.2.2      Time to ASAS20 and ASAS40 response**

A by-subject listing showing time to ASAS20 response and time to ASAS40 response will be presented by treatment group and visit for the FAS. This listing will include flags for censored observations.

The time to ASAS20 response and time to ASAS40 response during the Treatment Period and during the study (Treatment Period + Treatment Extension Period) will be summarized for the FAS separately using the following statistics:

- Number and percentage of subjects that are responders
- Number and percentage of subjects that are censored
- Minimum, maximum and Kaplan-Meier estimates of the 25th percentile, median and 75th percentile, with corresponding 95% CIs

Kaplan-Meier response rates for ASAS20 and ASAS40 will be presented for each treatment, including the cumulative number of events and the number of subjects at risk at each study visit.

This will be presented separately for the Treatment period and across the study (Treatment Period + Treatment Extension Period).

Kaplan-Meier curves will be presented for time to ASAS20 response and time to ASAS40 response for the Treatment Period and across the study (Treatment Period + Treatment Extension Period) separately, with both treatment groups overlaid on each plot. The plot will start at zero (ie, no responders at time zero) and be non-decreasing.

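### Whole-study time to ASAS20/ASAS40 censors subjects who leave without a response, although non-responders may be withdrawn at Week 12; the Kaplan-Meier curve after Week 12 may overstate response

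*SAP*

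**What the plan says.** SAP 8.3.1 defines time to ASAS20 response twice, once for the Treatment Period and once for the Treatment and Extension Periods together.

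- Whole study: "Subjects who discontinue early prior to an ASAS20 response will be censored on the date of their last efficacy assessment during the study". Subjects who stay without responding are censored at Week 48.
- First 12 weeks: "Subjects who do not have an ASAS20 response during the Treatment Period will be censored on the date of their Week 12 efficacy assessment".
- ASAS40: "the same censoring rules will be applied".

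SAP 8.3.2.2 reports quartiles of time to response, curves with both arms overlaid, and rates by visit: "Kaplan-Meier response rates for ASAS20 and ASAS40 will be presented for each treatment". The same summary includes "Number and percentage of subjects that are responders" and the number censored.

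Protocol 5.1.3, repeated in SAP 2.3, bars from the extension those withdrawn for lack of response: "Subjects not responding to treatment during the Treatment Period will be withdrawn from the study as per Investigator's discretion and will not enter". Non-response is not defined there and is not tied to ASAS20 or ASAS40. Protocol 5.9 gives as one purpose of the extension "to allow continued access to IMP for subjects responding to treatment".

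Neither document provides a competing-event analysis, a non-responder rule or a sensitivity analysis for the time-to-response estimates.

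**The concern.** Kaplan-Meier treats a censored subject as having the same later chance of response as those still followed. Under Protocol 5.1.3 a subject can be removed at Week 12 because he or she has not responded, so whether a subject is censored can depend on response. The subjects who remain at risk then stand in for subjects judged to be doing worse.

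At stake is how the whole-study curves after Week 12 are read, together with any percentile first reached after Week 12. If the two arms lose non-responders differently, the overlaid curves could also be distorted by different amounts.

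**Working it through.** **Inputs.** The documents state no ASAS response rate, no withdrawal rate and no target figure for this endpoint, so there is no planned figure to reproduce. The quantities below are assumptions:

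- R = share responding by Week 12
- w = share of Week 12 non-responders who are withdrawn
- r = share of those who stay who respond by Week 48
- rw = share of the withdrawn who would have responded by Week 48 had they stayed

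The formulas assume no other losses between Weeks 12 and 48.

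**Three quantities at Week 48, for w below 1**

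- Kaplan-Meier: 1 − (1−R)(1−r)
- Share who actually responded: R + (1−R)(1−w)r
- Share had all stayed: R + (1−R)[(1−w)r + w·rw]

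Subtracting gives two different gaps:

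- Kaplan-Meier minus actual responders = (1−R)·w·r
- Kaplan-Meier minus had all stayed = (1−R)·w·(r−rw)

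**Example: R = 0.6, w = 0.5, r = 0.5**

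- Kaplan-Meier: 1 − 0.4 × 0.5 = 80%
- Actual responders: 0.6 + 0.4 × 0.5 × 0.5 = 70%, a gap of 10 points
- Had all stayed with rw = 0.25: 0.6 + 0.4 × (0.25 + 0.125) = 75%, a bias of 5 points
- Had all stayed with rw = r = 0.5: 80%, a bias of 0

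**Range of the first gap.** Take R from 0.5 to 0.7, w from 0.25 to 0.75 and r from 0.3 to 0.5. The smallest value is 0.3 × 0.25 × 0.3 = 2.3 points and the largest is 0.5 × 0.75 × 0.5 = 18.8 points.

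**Boundary cases.** If nobody is withdrawn (w = 0), both gaps are zero. If every at-risk non-responder is withdrawn (w = 1), the risk set is empty after Week 12. The curve then stops at R and does not exceed the share who responded. For ASAS40 that boundary is less likely: even if every ASAS20 non-responder left, subjects with ASAS20 but not ASAS40 would still be at risk.

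**Percentiles.** In the example the 25th percentile and the median are reached by Week 12, so their point estimates do not move. The 75th percentile can move: Kaplan-Meier reaches 80% and so returns a value, while the share who responded stops at 70%.

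**Simulation.** The protocol visit schedule was simulated with 40 subjects per arm, about 54% responding by Week 12, and response probabilities that vary between subjects. Withdrawal at Week 12 was either selective (those least likely to respond) or random.

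| Non-responders withdrawn | Kaplan-Meier, Week 48 | Had all stayed | Observed responders |
|---|---|---|---|
| 25%, selective | 77.7% | 73.2% | 71.9% |
| 50%, selective | 82.8% | 73.3% | 68.5% |
| 75%, selective | 89.1% | 73.4% | 63.1% |
| 50%, random | 73.0% | 73.0% | 63.6% |

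Results with 20 per arm were nearly the same. Selective withdrawal biases Kaplan-Meier on either reading. Random withdrawal leaves it unbiased for the had-all-stayed quantity, although it still exceeds the share observed to respond. The selective case ranks subjects by their true probability of response, which is sharper than an Investigator could manage, so it marks the unfavourable end.

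**Small arms.** With 60 subjects at 2:1, the CZP arm has 20. Under the example rates 8 have not responded at Week 12 and 4 of them stay. Each late response then lifts the curve by 0.4/4 = 10 points, although one subject is 5% of the arm.

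**The case against.** The case for leaving the plan alone has real force.

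- Withdrawal is at the Investigator's discretion. A reader might infer that non-response is the main reason for leaving without a response. The documents do not say so, and Protocol 6.3 lists many other withdrawal criteria. A reader might also infer that the curves are necessarily too high; the boundary cases show that this does not follow.
- The 10 points, and the range of 2 to 19, compare Kaplan-Meier with the share who actually responded. That gap arises under random withdrawal too. It measures informative-censoring bias only if no withdrawn subject would ever have responded (rw = 0).
- SAP 8.3.2.2 already prints the responder percentage, the number censored, cumulative events and numbers at risk. Under the default denominator in SAP 3.1, that percentage is the 70% of the example.
- Protocol 4.1.3 labels the variable exploratory, and SAP 3.1 confines formal testing to the primary and secondary efficacy variables.
- Counting every leaver as a non-responder is itself an assumption and changes what is estimated.

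All of this limits the size and weight of the point. It does not remove it: the crude percentage corrects neither the curve after Week 12 nor a late percentile, and the same output could show 80% and 70% for one arm without explanation.

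**Conclusion.** The point holds, with minor severity. It is confined to the whole-study analysis after Week 12. The separate Treatment Period analysis, and percentiles reached by Week 12, are not affected by this mechanism.

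The upward bias needs two conditions: some but not all at-risk non-responders are withdrawn, and those withdrawn have a poorer outlook than those who stay. The documents make both plausible but establish neither, and supply no rates, so every figure above is illustrative.

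A reader might also infer that the arm with more non-responder withdrawals is always overstated more. That is not supported, because the gap depends on later response as well. An arm with 20% of its subjects withdrawn and r = 0.2 is overstated by 0.20 × 0.2 = 4 points; one with 10% withdrawn and r = 0.5 is overstated by 0.10 × 0.5 = 5 points. The arms may be distorted differently if R, w, r or rw differ between them, but the direction cannot be stated in advance.

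**What to change.** In SAP 8.3.1 and 8.3.2.2, for the whole-study analysis of ASAS20 and ASAS40, present the cumulative incidence of response with discontinuation without response as a competing event. Keeping such subjects at risk as non-responders to Week 48 is equivalent. Retain the current Kaplan-Meier display as a sensitivity analysis, and add a sentence saying what each estimate describes. The Treatment Period analysis need not change for this reason.

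The cost is one derivation and a few lines of SAP text, with no change to data collection or to the withdrawal rule. The downside is slight conservatism for subjects who leave for reasons unrelated to response. This is a cheap improvement.

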### **8.3.2        Presentation of Assessment in SpondyloArthritis International Society Response**

#### **8.3.2.1      ASAS20 and ASAS40 response**

A by-subject listing showing ASAS20 and ASAS40 response status will be presented by treatment group and visit for the FAS.

The number and percentage of subjects classified as ASAS20 and ASAS40 at each post-Baseline visit will be tabulated by treatment group for the FAS including the 95% CI calculated using a Wilson approximation.

#### **8.3.2.2      Time to ASAS20 and ASAS40 response**

A by-subject listing showing time to ASAS20 response and time to ASAS40 response will be presented by treatment group and visit for the FAS. This listing will include flags for censored observations.

The time to ASAS20 response and time to ASAS40 response during the Treatment Period and during the study (Treatment Period + Treatment Extension Period) will be summarized for the FAS separately using the following statistics:

- Number and percentage of subjects that are responders
- Number and percentage of subjects that are censored
- Minimum, maximum and Kaplan-Meier estimates of the 25th percentile, median and 75th percentile, with corresponding 95% CIs

Kaplan-Meier response rates for ASAS20 and ASAS40 will be presented for each treatment, including the cumulative number of events and the number of subjects at risk at each study visit.

This will be presented separately for the Treatment period and across the study (Treatment Period + Treatment Extension Period).

Kaplan-Meier curves will be presented for time to ASAS20 response and time to ASAS40 response for the Treatment Period and across the study (Treatment Period + Treatment Extension Period) separately, with both treatment groups overlaid on each plot. The plot will start at zero (ie, no responders at time zero) and be non-decreasing.

### **8.3.2.3 ASAS-PR**

A by-subject listing showing ASAS-PR response status will be presented by treatment group and visit for the FAS.

The number and percentage of subjects classified as ASAS-PR at each post-Baseline visit will be tabulated by treatment group for the FAS including the 95% CI calculated using a Wilson approximation.

## **8.3.3 Presentation of components of Assessment in SpondyloArthritis International Society**

### **8.3.3.1 Bath Ankylosing Spondylitis Functional Index**

The BASFI is a validated index used to determine the degree of functional limitation in subjects with AS. The BASFI questionnaire comprises 10 questions, each of which has a possible value ranging from 0 ("Easy") to 10 ("Impossible"). The first 8 questions evaluate activities related to functional anatomical limitations due to AS and the final 2 questions evaluate a subject's ability to cope with everyday life. The BASFI will be administered at all visits per the schedule of events.

The BASFI score is the arithmetic mean of the 10 individual scores giving a value between 0 and 10, with lower scores indicating better physical function.

Missing data for the BASFI questionnaire will be handled as described in [Section 4.2.1.5](#).

The BASFI results will be listed by treatment group and visit for each subject in the FAS including the results from each of the individual 10 questions, the BASFI score, changes from Baseline and percentage changes from Baseline in the BASFI score.

The full BASFI questionnaire is shown in [Section 14.2](#). A glossary of the BASFI questionnaire will be presented.

Observed values, changes from Baseline and percentage changes from Baseline in the BASFI score will be summarized by treatment group and visit for the FAS.

### **8.3.3.2 Total and nocturnal spinal pain numeric rating scale**

The pain experienced by subjects due to AS will be assessed by the following questions, referring to the average experience over the past week:

- Total pain in the spine: How much pain of your spine due to spondylitis do you have?
- Nocturnal spinal pain: How much pain of your spine due to spondylitis do you have at night?

The response to these questions will be rated by the subjects on a scale from 0 (no pain) to 10 (most severe pain) and the response will be recorded on the eCRF.

The Total and Nocturnal spinal pain scores will be listed by treatment group and visit for each subject in the FAS including changes from Baseline and percentage changes from Baseline.

Observed values, changes from Baseline and percentage changes from Baseline will be summarized by treatment group and visit for the FAS for each of Total and Nocturnal spinal pain scores.

#### **8.3.4 Physician's Global Assessment of Disease Activity**

The Investigator will assess the overall status of the subject with respect to their AS signs and symptoms and functional capacity (considering both joint and skin components) using an NRS where 0=very good, asymptomatic and no limitations of normal activities and 10=very poor, very severe symptoms which are intolerable and inability to carry out normal activities.

A by-subject listing will present the PhGADA results by treatment group and visit for the FAS, including changes from Baseline. Observed values and changes from Baseline will be summarized by treatment group and visit for the FAS.

#### **8.3.5 Hospital Anxiety and Depression Scale**

The HADS was chosen for its well-established psychometric properties and its use in clinical research on biological therapy in subjects with other inflammatory skin diseases (Dauden et al, 2009; Langley et al, 2010).

The HADS is a commonly used instrument to determine the levels of anxiety and depression that a subject is experiencing. The HADS is a 14-item scale that generates ordinal data. Seven items relate to anxiety (assessed in the HADS-A) and seven relate to depression (assessed in the HADS-D). Individual item scores range from 0 to 3 and are summed to give a total score on each of the individual HADS-A and HADS-D scales. These total scores range from 0 to 21 with higher scores indicating a worse state.

In case of missing data, the rules in [Section 4.2.1.6](#) will apply.

The full HADS questionnaire is shown in [Section 14.3](#). A glossary of the HADS questionnaire will be presented.

Scores for each item on the HADS-A and HADS-D will be listed at each visit by treatment group for each subject in the FAS. This listing will also include the total HADS-A and HADS-D scores together with the changes from Baseline in the total HADS-A and total HADS-D scores at each visit. Summary statistics will be presented by treatment group for the observed total HADS-A and HADS-D scores together with changes from Baseline at each visit for the FAS.

